9.2. Endpoint

9.2.1. Primary endpoint

Patient characteristics at baseline (at the initiation of 1L Cht and the initiation of avelumab maintenance therapy)

The following baseline (at the initiation of 1L Cht and the initiation of avelumab maintenance therapy) patient background will be collected. The latest data before the start of 1L Cht and before the start of avelumab administration will be collected, respectively.

- 1) Age*
- 2) Sex*
- 3) Medical history/comorbidity (interstitial lung disease/chronic obstructive pulmonary disease/autoimmune disease/cerebrovascular disease/cardiovascular disease/diabetes/others) *
If these diseases are cured by the start of avelumab administration, they are treated as a medical history, and if they continue after avelumab administration, they are treated as comorbidity.
- 4) Confirmed date of urothelial carcinoma
- 5) Eastern Cooperative Oncology Group (ECOG)
- 6) Tumor-node-metastasis (TNM) classification
- 7) Cht regimens received in 1L (Cisplatin [Cis]/ Gemcitabine [Gem], Carboplatin [Carbo]/Gem, Methotrexate, Vinblastine, Adriamycin, and Cisplatin [MVAC] regimens, dose dense-MVAC, others)
- 8) Start date and end date of administration, Number of Cht cycles received in 1L
- 9) Duration between the end date of 1L Cht and the start date of avelumab
- 10) Best overall response to 1L Cht (complete response [CR], partial response [PR], stable disease [SD], PD)
- 11) Site (bladder, urethra, renal pelvis or ureter) and histology (Urothelial carcinoma/ adenocarcinoma/ squamous cell carcinoma/ small cell carcinoma/others [details]) of the primary tumor at the time of initial diagnosis.
- 12) Histological atypia
- 13) Histological depth of tumor invasion
- 14) Definitive treatment of primary lesion (Yes [Surgery/ Others]/ No), date of treatment.

15) Site of distant metastasis (Yes [visceral/ non visceral]/ No)

Visceral: Having to do with the viscera, which are the soft internal organs of the body, including the lungs, the heart, and the organs of the digestive, excretory, reproductive, and circulatory systems (Classified as "visceral" if it has visceral metastasis, and classified as "non-visceral" if it has only locally advanced / recurrent lesions and non-visceral lesions without visceral metastasis)

16) Local recurrence (Yes/No), if yes, recurrence confirmed date

17) Bajorin risk classification (0/1/2)

<Bajorin risk classification¹⁰>

Risk factor	Classification	
• Visceral metastases	No risk factor	0

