5.2 Handling of missing values

An absence of data for analysis will be treated as missing values, and no special imputation processing will be performed using statistical methods.

However, if there are specifications for handling of missing values in subsequent each specification, they are followed.

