5.3 Handling of data on the number of days

The number of days from the start date to the target date will be calculated as follows:

- The target date is earlier than the start date = Target date – Start date
- The target date is on or after the start date = Target date – Start date + 1

If the data for "year" and "month" among the date data are missing, no calculation will be performed.

If the data on "day" of the date is missing, data will be substituted by 1.

The number of days in one month is converted to 30.

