5.5 Derived variable

The items and definitions of variables whose derivation is necessary at the time of statistical analysis are shown below.

Continuous variable

Item	Derivation method
Treatment-free interval: Time from the end date of first-line chemotherapy to the start date of avelumab administration (days)	Start date of initial administration with avelumab – end date of first-line chemotherapy administration + 1
Duration of treatment of first-line chemotherapy (days)	End date of first-line chemotherapy administration – start date of first-line chemotherapy administration + 1
Duration of treatment (irAE treatment) of corticosteroid (days)	End date of corticosteroid administration – start date of corticosteroid administration + 1
Time to treatment failure of avelumab (TTF)	Defined as the period from the date of start of avelumab to the date of end of treatment* for any reasons including death. If there is no record of end of treatment, patients will be censored at the date of last observation during the study period. *The following sensitivity analysis will also be performed. Considering its clinical meaning, "interruption due to being well-controlled" does not correspond to "treatment failure"; it should be treated as an event on the day when the death or discontinuation was observed prior to the last observation date. If no death or discontinuation occurred before the date of the last observation, data will be censored at the date of the last observation.
Real-world progression-free survival (rwPFS)	Defined as the period from the start date of avelumab maintenance therapy to the date of first

	
disease progression (clinical evaluation based on imaging examinations, laboratory tests, and pathological tests, as well as other evaluations by the investigators of each institution) or death from any cause, whichever occurs earlier.
 
If there is no record of death or disease progression, patients on second or later lines (following avelumab maintenance therapy) will be censored at the start of the second-line treatment, and patients on only avelumab maintenance therapy will be censored at the date of the last visit during the study, based on the medical record.

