	Primary tumor (T factor)	Reginal lymph nodes (N factor)	Distant metastasis (M factor)	Clinical stage
	Ta	N0	M0	0a
	Tis	N0	M0	0is
	T1	N0	M0	I
	T2	N1	M0	II
	T1, T2	N1	M0	III
	T3	N0, N1	M0	III
	T4	N0, N1	M0	IV
Clinical stage classification: Renal pelvis, Ureter	Any T	N2	M0	IV
	Any T	Any N	M1	IV
	Clinical stage is categorized using primary tumor (T factor), reginal lymph nodes (N factor), distant metastasis (M factor) as follows.			
	Primary tumor (T factor)	Reginal lymph nodes (N factor)	Distant metastasis (M factor)	Clinical stage
	Ta	N0	M0	0a
	Tis	N0	M0	0is
	T1	N0	M0	I
	T2	N0	M0	II
	T3	N0	M0	III
Treatment-free interval: Time from the end date of first-line chemotherapy to the start date of avelumab administration (3 divisions)	T4	N0	M0	IV
	Any T	N1、N2	M0	IV
	Any T	Any N	M1	IV
Response (avelumab maintenance)	Time from the end date of first-line chemotherapy to the start date of avelumab administration is divided into the following categories. <4 weeks/4 to 10 weeks/>10 weeks			
	Determination of the best overall response to avelumab maintenance is categorized as following: "Objective response" when "CR" or "PR." "Non-objective response" when "SD" or "PD"			
	Determination of the best overall response to first-line chemotherapy is categorized as following:			

	
"Objective response" when "CR" or "PR."
 
"Non-objective response" when "SD" or "PD"

Best overall response to first-line chemotherapy (2)	Determination of the best overall response to first-line chemotherapy is categorized as following: CR + PR/SD
Presence or absence of prednisolone	"Presence" will be selected when "prednisolone" is selected for the corticosteroid administration drug name, and "absence" will be selected when "No" is selected for the drug name.
Presence or absence of methylprednisolone	"Presence" will be selected when "methylprednisolone" is selected for the corticosteroid administration drug name, and "absence" will be selected when "No" is selected for the drug name.
Presence or absence of betamethasone	"Presence" will be selected when "betamethasone" is selected for the corticosteroid administration drug name, and "absence" will be selected when "No" is selected for the drug name.
Presence or absence of dexamethasone	"Presence" will be selected when "dexamethasone" is selected for the corticosteroid administration drug name, and "absence" will be selected when "No" is selected for the drug name.

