6.3.2 Number of digits

Percentages will be rounded to 1 decimal place for the fraction distribution, unless the details of the individual items are specified. Among the summary statistics (number of subjects, mean standard deviation, minimum value, quartiles (25% point, 50% point [median], 75% point), and maximum value), the mean, standard deviation, and quartiles (25% point, 50% point [median], 75% point) are rounded up to where a decimal place is one digit below the original data.

7 Analysis of primary endpoints

7.1 Patient characteristics at baseline (at the start of the first-line chemotherapy and at the start of the avelumab administration)

Target : Analysis set

populatio

n

Endpoints : 1) Primary lesion at initial diagnosis

Categorical Variable

Site of the primary tumor
Histology of primary lesion¹⁾
Presence or absence of variant histology
 Subtype
Histologic dysplasia
 Two-step grade
 Three-step grade
Histological depth
Presence/absence of definitive treatment of primary lesion
 Treatment
 Surgery

2) At the start of the first-line chemotherapy

Continuous variable

Number of cycles of first-line chemotherapy
Number of cycles at the evaluation of best overall response to first-line chemotherapies
Treatment-free interval: Time from the end of first-line chemotherapy to the start date of avelumab administration (days)
Duration of first-line chemotherapy (days)

Categorical Variable

ECOG Performance Status
Karnofsky performance status (%)
Karnofsky performance status (2 divisions)
Bajorin risk classification
Staging (TNM classification)
 Primary tumor (T factor)
 Metastases to regional lymph nodes (N factor)
 Distant metastasis (M factor)
Clinical Stage
 Bladder
 Urethra
 Renal pelvis and ureter
Presence/absence of distant metastasis

distant metastasis site
Presence or absence of visceral metastasis
Presence or absence of non-visceral metastasis
Number of metastatic organs
Number of metastases in one organ
Number of distant metastases
Presence/absence of local recurrence
Regimen for first-line chemotherapy
Best overall response to first-line chemotherapies

3) At the start of avelumab administration

Continuous variable

Age

Categorical Variable

Gender
ECOG Performance Status
Karnofsky performance status (%)
Karnofsky performance status (2 divisions)
Bajorin risk classification
Staging (TNM classification)
 Primary tumor (T factor)
 Metastases to regional lymph nodes (N factor)
 Distant metastasis (M factor)
Clinical Stage
 Bladder

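### The SAP's urethral stage table gives T2 N1 M0 two stages and T2 N0 M0 none; secondarily, the treatment-free interval runs one day long and the missing-day rule can yield negative event times

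*SAP*

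**What the plan says.** **Stage.** SAP 5.5 maps T, N and M to clinical stage in three tables: bladder, urethra, and renal pelvis/ureter. In the urethra table the stage II row is T2, N1, M0. The next row puts T1 or T2 with N1, M0 in stage III. No row contains T2 with N0 and M0. SAP 7.1 allows N0 as a urethral value and tabulates urethral clinical stage at both baselines: start of first-line chemotherapy and start of avelumab.

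**Treatment-free interval.** Protocol 9.2.1 lists as a baseline item the "Duration between the end date of 1L Cht and the start date of avelumab". SAP 5.5 computes it as "Start date of initial administration with avelumab – end date of first-line chemotherapy administration + 1", in line with the general day count in SAP 5.3: "The target date is on or after the start date = Target date – Start date + 1". SAP 7.1 summarises it as a continuous variable in days. SAP 5.5 also defines a three-category version, "<4 weeks/4 to 10 weeks/>10 weeks", which does not appear in the SAP 7.1 lists.

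**Partial dates.** SAP 5.2 rules out statistical imputation, with a carve-out: "However, if there are specifications for handling of missing values in subsequent each specification, they are followed". SAP 5.3 uses it: if the day "of the date is missing, data will be substituted by 1". No bound against other recorded dates is given.

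**The concern.** The primary objective is purely descriptive, so correct derivation of the baseline variables is itself the deliverable.

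The urethra table fails on its own terms: one TNM combination has two answers and another, fully valid, has none. A programmer following the SAP must choose a stage without guidance, and two programmers could choose differently.

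Adding 1 suits a treatment duration, where the first and last days are both treated. The treatment-free interval is the reverse: it lies between two treated days, and the +1 counts both as treatment-free.

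Setting a missing day to the 1st always chooses the earliest possible date. For a chemotherapy end date this lengthens the treatment-free interval. For an avelumab start date it shortens it. For a progression, discontinuation or death date it shortens TTF or rwPFS, and can place the event before treatment began.

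**Working it through.** The plan states no numerical result here, so the check is to apply its rules as written.

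**1. Urethral stage (SAP 5.5, with the values allowed in SAP 7.1).** Each combination of T0/Ta/Tis/T1/T2/T3/T4, N0/N1/N2 and M0/M1 was looked up and the matching rows counted.

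| Combination | Matching rows as printed | If the stage II row read N0 |
|---|---|---|
| T2 N0 M0 | none | one (II) |
| T2 N1 M0 | two (II and III) | one (III) |
| T0 N0 M0, T0 N1 M0, Ta N1 M0, Tis N1 M0 | none | none |
| all others | one | one |

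The comparison rows point to N0. The bladder table gives T2a/T2b N0 M0 as II, the renal pelvis/ureter table gives T2 N0 M0 as II, and the urethra table's own stage I row pairs T1 with N0. The other two tables contain no double assignment. They do have gaps: T0 N0 M0 matches no row in any table, and in the bladder table T0, Ta and Tis with N1 to N3 and M0 also match none.

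**2. Treatment-free interval.** Let g = avelumab start − chemotherapy end, in elapsed days. The SAP value is g + 1. With 7-day weeks and no rounding (assumptions; the SAP gives no week conversion), the cuts fall at 28 and 70 days.

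| g | Category of g | SAP value | Category of SAP value |
|---|---|---|---|
| 27 | under 4 weeks | 28 | 4 to 10 weeks |
| 28 | 4 to 10 weeks | 29 | 4 to 10 weeks |
| 69 | 4 to 10 weeks | 70 | 4 to 10 weeks |
| 70 | 4 to 10 weeks | 71 (71/7 = 10.14 weeks) | over 10 weeks |

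The middle category therefore holds elapsed gaps of 27–69 days instead of 28–70. Among whole-week gaps from 2 to 14 weeks, only the 10-week gap changes category. If gaps were uniform over the 85 values 14–98 days (an illustration), 2/85 = 2.4% of patients with complete dates would change.

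**3. Missing day set to 1.** The shift is (true day − 1), so 0 to 30 days; its mean over the days of 2021 is 14.7. Example: avelumab starts on 10 March and death is recorded as March, day missing. The imputed date is 1 March. SAP 5.3 then takes target − start without +1, giving 1 − 10 = −9 days.

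For scale only, assume chemotherapy end dates uniform over 2021, gaps uniform over 14–98 days, and the end day missing. The share of such patients whose category differs from that of the true elapsed gap is then:

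- day 1 with the +1: about 31%
- day 1 without the +1: about 30%
- day 15 without the +1: about 18%

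Nearly all of the difference comes from the day rule; the +1 adds under 2 percentage points.

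**The case against.** **The +1 is a declared convention.** SAP 5.3 adds 1 to every forward interval and SAP 5.5 follows it. That stands: this is not an internal contradiction. It is still a poor fit for a gap between two treated days. A reader might infer that the primary analysis misclassifies patients at 10 weeks. The documents do not support this, because SAP 7.1 lists the interval only in days and any use of the three-category version is not visible. The visible effect on the primary endpoint is 1 day. Nor do the documents support any clustering of gaps on whole weeks.

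**Day 1 is openly specified and SAP 5.2 permits it.** That also stands. Sites enter data from charts and answer queries against source (Protocol 9.7), so partial dates may be rare. A reader might take 31% as the share of patients misclassified. It applies only to patients with a missing chemotherapy end day, rests on assumed distributions, and would still be about 18% with a mid-month date.

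**A tempting cure would do harm.** Forcing every imputed event after the last documented alive date would push progression to or past last follow-up and lengthen rwPFS, since progression normally precedes that date. Nor is a progression date before a later dose an error in itself: TTF and rwPFS are separate endpoints, and their definitions do not tie progression to the end of dosing.

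**Correcting one staging row does not close the table.** This is true; several T0, Ta and Tis combinations still match no row. It is a reason to extend the correction, and it leaves the T2 contradiction in place. Table layout can suffer in conversion from PDF, so the row should be confirmed against the SAP page, but nothing in the text suggests that the character was misread.

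**Conclusion.** The urethral stage rule is wrong as written: T2 N1 M0 has two stages and T2 N0 M0 has none, in a variable tabulated at both baselines of the primary analysis. This rests only on the SAP's own tables. It affects only urethral primaries staged T2 N0 M0 or T2 N1 M0, expected to be few.

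The other two points are real but secondary. The continuous treatment-free interval is 1 day too long for every patient. The shift of the middle category from 28–70 to 27–69 days assumes unrounded 7-day weeks and matters only where the three-category variable is used. The day-1 rule pulls each partial date back by 0 to 30 days, about 14.7 on average, and can produce a negative event time. Its overall effect cannot be sized without the rate of partial dates. None of this shows that the study's descriptive or time-to-event results would change materially. The corrections should be made because they are cheap and the rules as printed are defective.

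**What to change.** **Stage.** In the SAP 5.5 urethra table, change N1 to N0 in the T2 stage II row and keep the row that puts T1 or T2 with N1, M0 in stage III. Add an unclassifiable category to all three tables for TNM combinations that match no row, such as T0 N0 M0 or urethral Ta/Tis N1 M0.

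**Treatment-free interval.** Define it as avelumab start minus last chemotherapy date, without +1. State that a week is 7 days and that values are not rounded before categorising.

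**Partial dates.** At minimum, do not let an imputed progression, discontinuation or death date fall before avelumab start, and do not let an imputed death date fall before the last documented alive date. Do not bound progression by the last alive date. Report the number of imputed dates for each variable.

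**Cost.** Three short SAP edits and a few lines of code, with no new data. Protocol 9.8 requires the SAP to be final before data lock; the dataset lock is planned for 31 January 2023 (Protocol section 6), and SAP version 1.1 is dated 21 December 2022.

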9.2.2. Secondary endpoints

Efficacy endpoint

- Time to treatment failure (TTF) of avelumab

Definition of TTF is provided in 20. The following avelumab treatment data will be collected:

- 1) Date of start and end of avelumab administration
- 2) Dosage of avelumab
- 3) Date of avelumab discontinuation and interruption
- 4) Reason for avelumab discontinuation and interruption
- 5) Date of last survival confirmation

- Real-world progression-free survival (rwPFS)

Definition of rwPFS is provided in 20. The following data will be collected:

- 1) Date of start of avelumab treatment (administration)
- 2) Date of first disease progression or death due to any cause, whichever came first
- 3) Date of last survival confirmation

- Objective Response Rate (ORR)

ORR is defined in 21. The following data will be collected:

- 1) Tumor assessment (CR, PR, SD, PD)

- rwPFS from chemotherapy (rwPFS-c)

Definition of rwPFS-c is provided in Section 9.2.3.4. The following data will be collected:

- 1) Date of start of 1L Cht (administration)

- 2) Date of first disease progression or death due to any cause during avelumab treatment, whichever came first
- 3) Date of last survival confirmation

Safety endpoints

- Corticosteroid therapy for immune-related adverse events (irAEs)
The following data will be collected:
 - 1) Date of treatment
 - 2) Drug name of corticosteroid
 - 3) Starting dose of corticosteroid
 - 4) Duration of corticosteroid treatment
- Premedication for potential infusion-related reaction of avelumab
The following data will be collected:
 - 1) Presence of premedication for infusion-related reaction of avelumab
 - 2) Drug name used for premedication for infusion-related reactions of avelumab
- Treatment for infusion-related reaction of avelumab
The following data will be collected:
 - 1) Presence of treatment for infusion-related reaction of avelumab
 - 2) Drug name used for treatment for infusion-related reaction of avelumab
- Regimen after avelumab maintenance therapy
The following data will be collected:
 - 1) Medication for UC after avelumab maintenance therapy (drug name, start date of treatment, end date of treatment)
- Hematological test (after the start of 1L Cht)
The following data will be collected:
 - 1) Red blood cell count/ hemoglobin/ hematocrit/ white blood cell count (neutrophils, eosinophils, basophils, monocytes, lymphocytes)/ platelet count/ C-reactive protein (CRP)/ total protein/ albumin/ AST/ ALT/ LDH/ BUN/ creatinine/ Na/ K/ Cl

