9.2.3. Definition of endpoints

9.2.3.1. Time to treatment failure (TTF)

TTF is defined as the following:

TTF, defined as the time from start of avelumab maintenance therapy to the date of end of treatment due to any cause including death. If there is no record of the end of treatment, it be discontinued on the last observation date during the study period.

9.2.3.2. rwPFS

rwPFS is defined as the following:

The time from start of avelumab maintenance therapy to date of first disease progression (as

clinically assessed by local investigator based on radiology, laboratory evidence, pathology, or other assessments) or death due to any cause, whichever occurred first. If there were no clinical records of death or disease progression, they will be censored at the date of initiation of the next line of therapy for the patients undertaking 2 or more lines of therapy (subsequent therapy after avelumab maintenance therapy) based on the record, or at their last observation date during the study period for the patients undertaking only 1 line of therapy (only avelumab maintenance therapy) based on the record.

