9.2.3.3. Objective response rate (ORR)

OR is defined as the following:

Complete or partial response as the best adjudication result (CR > PR > SD > PD) in a method that complies with Response Evaluation Criteria in Solid Tumors (RECIST) version. 1.1 tumor assessment as closely as possible in clinical practice by investigator's judgment.

9.2.3.4. rwPFS-c

rwPFS-c is defined as the following:

The time from start of 1L Cht to date of first disease progression (as clinically assessed by local investigator based on radiology, laboratory evidence, pathology, or other assessments) or death due to any cause during avelumab treatment, whichever occurred first. If there were no clinical records of death or disease progression, they will be censored at the date of initiation of the next line of therapy for the patients undertaking 2 or more lines of therapy (subsequent therapy after avelumab maintenance therapy) based on the record, or at their last observation date during the study period for the patients undertaking only 1 line of therapy (only avelumab maintenance therapy) based on the record.

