Real-world progression-free survival from chemotherapy (rwPFS-c)	
Defined as the period from the start date of first-line chemotherapy to the date of first disease progression (clinical evaluation based on imaging examinations, laboratory tests, and pathological test, as well as other evaluations by the investigators of each institution) or death from any cause, whichever occurs earlier.
 
If there is no record of death or disease progression, patients on second or later lines (following avelumab maintenance therapy) will be censored at the start of the second-line treatment, and patients on only avelumab maintenance therapy will be censored at the date of the last visit during the study, based on the medical record.

Starting dose of corticosteroid (Steroid equivalent dose)	Calculate according to “5.4 Steroid equivalent dose (prednisolone-equivalent dose.”
Duration of treatment of corticosteroid (days)	Last administration date – date of first administration of the first steroid drug + 1
Duration of treatment of avelumab maintenance (days)	Last administration date – date of first administration + 1.
Duration of treatment of each regimen (days)	Last administration date – date of first administration + 1.

Categorical variable

Item	Derivation method
Age (2 divisions)	Age is divided into the following categories: <65 years/65 years or older
Site of primary tumor (2 divisions)	The primary site is divided into the following categories: "upper urinary tract" for renal pelvis or ureter "lower urinary tract" for bladder and urethra
Tumor histological type (2)	The histological types are divided into the following categories. "Urothelial carcinoma" for urothelial carcinoma "Non-urothelial carcinoma" for adenocarcinoma, squamous cell carcinoma, small cell carcinoma, or others
Presence or absence of visceral metastasis	"Presence" will be selected if the metastatic site is "lung," "liver," "adrenal gland," "pancreas," "kidney," "spleen," or "other" which is regarded as visceral metastasis. If the metastatic site is not regarded as visceral metastasis, "absence" will be selected.
Presence or absence of non-visceral metastasis	"Presence" will be selected if the metastatic site is "bone," "distant lymph nodes," or "other" which is regarded as non-visceral metastasis. If the metastatic site is not regarded as non-visceral metastasis, "absence" will be selected.

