8.1.2 Real-world progression-free survival (rwPFS)

Target : Analysis set

population

n

Endpoint : **Real-world progression-free survival (rwPFS)**

Statistical analysis : For the endpoint, the median and its 95% confidence interval will be calculated using the Kaplan–Meier method. In addition, the Kaplan–Meier curve will be plotted, and the rwPFS rate for every 2 months and its 95% confidence interval will be calculated. Greenwood’s formula will be used to calculate the confidence interval for the rwPFS rate.

In order to evaluate the overall observation period of the study, the median observation period will be calculated by estimating the reverse KM curve in which censoring patients are regarded as patients with events and patients with events are regarded as censoring patients.

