8.2.4 Regimen after avelumab maintenance therapy

Target : Analysis set
population

n

Endpoint : Continuous variable
Duration of Treatment after avelumab maintenance therapy (Days)

Categorical variable

Presence/absence of UC treatment after avelumab maintenance therapy
Regimen after avelumab maintenance therapy

Statistical analysis : The following aggregation will be performed for the end point.
For continuous variables, summary statistics will be calculated for each treatment. A frequency table (number of subjects, proportion (%)) will be created for the presence or absence of UC treatment after avelumab maintenance therapy.
A frequency table (number and proportion (%)) will be created for the second-line, third-line and subsequent treatment regimens for the second-line and subsequent treatment after avelumab maintenance therapy.

In addition, a listing of patients will be prepared.

【Division of categorical variables】

Factor	Division
Presence or absence of treatment after avelumab maintenance therapy	Absence/Presence/Unknown/Missing

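### rwPFS, and rwPFS-c as the SAP defines it, are censored at next-line start only when no progression or death is recorded, with no limit to earlier records, so a later outcome decides whether time after the switch counts

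*SAP*

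**What the plan says.** In SAP 5.5 the rwPFS event is first progression "or death from any cause, whichever occurs earlier". The event is not confined to the period before a next line. The censoring rule follows: "If there is no record of death or disease progression, patients on second or later lines (following avelumab maintenance therapy) will be censored" at second-line start. Patients who received avelumab maintenance only are censored at their last visit.

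Protocol 9.2.3.2 agrees on the condition: "If there were no clinical records of death or disease progression, they will be censored at the date of initiation of the next line". The SAP uses the same event and the same rule for rwPFS-c, with the clock starting at first-line chemotherapy. Protocol 9.2.3.4 has the same censoring sentence for rwPFS-c but a narrower event clause: "or death due to any cause during avelumab treatment, whichever occurred first".

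Observation runs to 30 June 2022 for everyone, whether or not a next line starts (protocol 9.1, SAP 3.3), so progression or death after a switch can be on record. SAP 8.1.2 builds a Kaplan-Meier median on this variable, and "the rwPFS rate for every 2 months and its 95% confidence interval will be calculated". SAP 8.1.4 does the same for rwPFS-c.

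For later therapy, SAP 8.2.4 tabulates "Presence/absence of UC treatment after avelumab maintenance therapy" and adds: "In addition, a listing of patients will be prepared". Neither output is split by whether progression had already been recorded.

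**The concern.** Kaplan-Meier requires that leaving the risk set at a given time does not depend on what happens to the patient afterwards. The written condition breaks this for patients who start a next line with no earlier recorded progression. Those who later have an event stay in the risk set through the post-switch period. Those who do not are removed retrospectively at the switch. The denominators at later times therefore lose event-free patients selectively, and more patients do not cure it.

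Two of the four efficacy endpoints under secondary objective 1 depend on the rule. The reverse Kaplan-Meier observation time in SAP 8.1.2 and 8.1.4 uses the same dates and is affected too.

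**Working it through.** The visible plan states no expected rwPFS, event count or switching share, and the sample size is redacted, so there is no planned figure to reproduce. The only documented inputs are dates. From 30 November 2021 and 24 February 2021 to 30 June 2022 is 212 and 491 days, or 7.07 and 16.37 months of 30 days (SAP 5.3). Everything else below is an assumption.

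**1. Hand example.** Of 100 patients, 20 switch at month 3 without progression; 8 of these progress at month 9 and 12 stay event-free. Of the other 80, 32 progress at month 9.
- Written rule: the 12 leave at month 3, giving 1 − 40/88 = 54.5%.
- Follow everyone through: 1 − 40/100 = 60%.
- Censor every switcher at month 3: 1 − 32/80 = 60%.

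**2. Direction.** Against following everyone through, the events are identical and the risk set at each event time is equal or smaller. Every Kaplan-Meier factor is therefore equal or smaller, and the written curve can never be higher. Against censoring all switchers, there is no such guarantee. Take six patients with events at months 2, 3, 4, 5, 6 and 9, where the month-6 patient switched at month 1. At month 5 the written rule gives 2/6 = 33% and censoring all switchers gives 1/5 = 20%. In 4,000 simulated datasets (assumed n = 100, median 6 months, 4.6% switching) the written estimate was lower than censor-all in 84.5% at month 12, but higher in 46.0% at month 2.

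**3. Size in large samples.** Assume an exponential event time with median 6 months (h = ln 2/6), a constant switching hazard λ per month, hazard unchanged after the switch, and end of follow-up C uniform over 7.07-16.37 months. Let S(t) = exp(−ht) and G(t) = P(C > t). The risk set under the written rule is

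R(t) = S(t)G(t) − (1 − exp(−λt)) · E[S(C); C > t],

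where the subtracted term is the switchers who remain event-free to the end. The written curve is exp(−∫ h·S·G/R). Both consistent rules (follow through, censor all) give exp(−12h) = 25.0% at 12 months. Counting the switch as an event gives exp(−12(h + λ)).

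| λ | Switch in follow-up | Written | Consistent rules | Switch as event | Written median (months) |
|---|---|---|---|---|---|
| 0.005 | 3.1% | 24.4% | 25.0% | 23.5% | 5.96 |
| 0.0075 | 4.6% | 24.0% | 25.0% | 22.8% | 5.94 |
| 0.015 | 8.8% | 23.1% | 25.0% | 20.9% | 5.89 |
| 0.03 | 16.6% | 21.3% | 25.0% | 17.4% | 5.79 |

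Simulation with 1,000,000 patients per row agrees to about 0.1 point. At month 2 the gap is at most 0.2 points. With a median of 12 months and 4.1% switching, the 12-month rate is 49.2% against 50.0%, and the median 11.7 against 12.0 months.

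If the hazard halves or doubles after the switch (4.6% switching), the written rate is 24.4% or 23.6%, follow-through 26.0% or 24.0%, and censor-all 25.0% in both.

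For the SAP's rwPFS-c, with chemotherapy-to-avelumab time assumed uniform over 3-6 or 4-8 months, the 18-month rate at 4.5-4.6% switching is 20.0% against 21.0-21.1%, or 24.3% against 25.2-25.3%.

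**4. Scale.** At an assumed n = 100, the Greenwood 95% half-width at 12 months is 1.96 × 0.25 × √(∫ h/(S·G) / 100) ≈ 9.6 points.

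**5. If some switches hide unrecorded progression** (true 12-month rate 25%, simulated):

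| Genuine + hidden switches | Written | Censor all | Follow through | Switch as event |
|---|---|---|---|---|
| 4.6% + 3.5% | 25.0% | 26.8% | 26.7% | 22.9% |
| 8.9% + 1.4% | 23.5% | 25.7% | 25.7% | 20.9% |
| All hidden (5-20% of progressions) | 26.0-30.5% | 26.8-33.1% | 26.7-34.9% | 25% |

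**The case against.** The authors may have meant no record before the next line. The narrower event clause in protocol 9.2.3.4 points that way: if its limit to the avelumab treatment period covers progression as well as death, events after a switch do not count and the rule becomes ordinary censoring at the switch. That is a fair reading of the protocol's rwPFS-c, but it does not settle rwPFS, and the SAP drops the limit. Two readings that give different curves are themselves a reason to clarify.

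The effect may also be negligible. It needs patients who start a next line with no recorded progression, although progression may be recorded on broad clinical grounds. At 3-5% switching the shift is about 1 point at 12 months and 0.04-0.06 months in the median, well inside sampling error at an assumed n = 100. The endpoints are secondary, in a non-comparative chart review. This stands, and it limits the weight of the point.

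A reader might go further and infer that rwPFS will end up too low against true PFS, or that a consistent rule must bring it closer. Neither follows. With a mix of genuine and hidden switches the written rule's net error can be upward, near zero or downward, and in the first mix above it is the least biased of the four. What a consistent rule gains is internal consistency, not proven accuracy. Nor does counting the switch as an event correct for unrecorded progression: it returned 25% only when every switch was hidden.

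Finally, the visible text gives a sensitivity analysis for TTF alone, but parts of the SAP are redacted, so it cannot be said that none exists for rwPFS.

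**Conclusion.** The point holds on the wording. Taken literally, the rule lets later outcome decide whether post-switch time counts, and the Kaplan-Meier estimate is biased whenever patients switch without prior recorded progression. The curve is never higher than with full follow-through, and is generally lower at later times than with all switchers censored.

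The size cannot be determined from the documents. It is zero with no such switchers. With an assumed 6-month median and unchanged hazard it is about 1 point at 12 months for 3-5% switching, and about 4 points for 16-17%. The documents give no basis for the higher shares. No claim is made about the net distance from true PFS.

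It should be fixed because the wording allows two different curves and the repair is small, not because a large error has been shown.

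**What to change.** In SAP 5.5 (rwPFS and rwPFS-c) and protocol 9.2.3.2, apply one rule to all switchers. For example:

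> A patient with no progression or death recorded on or before the start of next-line therapy is censored at that start, whatever is recorded later.

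Following all patients to event or last observation is equally consistent. Run the rule not chosen as a sensitivity analysis. Run next-line start as an event as a further one, labelled a pessimistic bound and not a correction for unrecorded progression. Report how many patients start a next line without prior recorded progression.

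In the same edit, reconcile two wording differences: the rwPFS-c event (protocol 9.2.3.4 carries the avelumab-treatment limit, the SAP does not), and the censoring date for patients on avelumab only (last visit in the SAP, last observation date in the protocol).

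The cost is one clause per definition, including protocol 9.2.3.4 if it is aligned, a few lines of code, and extra runs for two endpoints. No new data are needed, since protocol 9.2.2 already collects "Medication for UC after avelumab maintenance therapy (drug name, start date of treatment, end date of treatment"). If censoring at the switch is chosen, events after a switch drop out and intervals widen slightly.
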